The primary objective of this proposed project is to evaluate the effectiveness of MF nasal saline irrigation as compared to the commonly used MF nasal spray in the medical management of CRS symptoms in patients who have not undergone sinus surgery.

Specifically, we propose:

1. Compare the effectiveness of MF nasal irrigation to that of MF nasal spray in the management of CRS symptoms in surgery-naïve, non-polyp patients.

Participants will be randomized to either 1) 8-weeks of MF nasal saline irrigation *and* placebo nasal spray or 2) MF nasal spray *and* nasal saline irrigation. The primary outcome measure will be the within subject changes in SNOT-22 scores pre-and post-treatment. We hypothesize that MF nasal saline irrigation, when compared to that of MF nasal spray alone, will be more effective in the treatment of CRS symptoms.

2. Evaluate the effect of MF nasal saline irrigation on the HPA axis compared to MF nasal spray 10 participants will be sampled from each study arm in order to ascertain the effect of mometasone nasal irrigation on the function of the hypothalamus-adrenal-pituitary (HPA) axis, as measured by the cosyntropin test before and after completion of intervention. In prior studies on the safety of MF nasal spray in children and adults, no discernible effects of MF nasal spray on the function of the HPA axis were reported.²⁹ To our knowledge, a study examining the impact of MF nasal saline irrigation on the HPA axis has not been performed. Based on prior studies demonstrating the safety of MF nasal spray, we hypothesize that MF nasal saline irrigation will have a negligible effect on the HPA axis. Furthermore, subjects will be queried throughout their participation in the study regarding any adverse events experienced with mometasone.

III. Experimental Plan, Methods, and Data Analysis

Study Design: Randomized clinical trial

Subjects: Up to 50 adult patients with complaints of purulent nasal drainage accompanied by nasal obstruction, facial pain-pressure-fullness, or both and reduction or loss of smell for 12 weeks or greater.

Inclusion Criteria:

Adults 18-70 years of age

Twelve (12) weeks or longer of two or more of the following signs and symptom consistent with chronic rhinosinusitis (CRS)^{30,31}.

mucopurulent drainage (anterior, posterior, or both), nasal obstruction (congestion), facial pain-pressure-fullness, and decreased sense of smell

AND inflammation documented by one or more of the following findings:

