Subjects randomized to the mometasone nasal irrigation intervention arm will be required to mix 2.4 mg of mometasone into the sinus rinse bottle and rinse each nasal cavity with one half of the bottle (~ 4 ounces or ~120 ml) daily. The inert ingredients are: loxasperse powder, which increases solubility and dispersibility of mometasone and is microbiologically safe; mannitol, which is widely used in pharmaceutical products as a capsule diluent; and Xylifos™ powder, which is a proprietary powder excipient used safely in pharmaceutical compounding for nasal nebulization or nasal irrigation.

Placebo Nasal Spray

The placebo nasal spray will be packaged in the same bottle as that of MF nasal spray. The nasal spray will be prepared by Advanced Rx Pharmacy and will contain the same inert ingredients found in MF nasal spray: glycerin, microcystalline cellulose and carboxymethylcellulose sodium, sodium citrate, citric acid, benzalkonium chloride, and polysorbate 80. Subjects in the mometasone nasal irrigation arm will be instructed to first irrigate with mometasone followed by use of the placebo nasal spray.

Mometasone Nasal Spray

Subjects randomized to the mometasone spray intervention arm will receive a 2 month supply of MF nasal spray (50 mcg/spray), which is commercially available as Nasonex™, but will be prepared for the study by Advanced Rx Pharmacy. Participants will be instructed to use 2 sprays per nostril once a day followed by nasal saline irrigation

Placebo Nasal Irrigation

The placebo product will contain lactose monohydrate and will be supplied in clear plastic capsules, which are identical to the budesonide capsules. The capsules will only contain lactose as there are no other ingredients.

Cosyntropin Test

Measuring blood levels of cortisol after cosyntropin stimulation is the gold standard to evaluate effects of exogenous corticosteroids on the HPA axis. The effects of mometasone nasal spray on the hypothalamus-pituitary-adrenal (HPA) axis have been evaluated in 6 clinical trials in both adults and children (dose range 100 ug once daily to 400 ug twice daily). In all 6 trials, no effects of mometasone nasal spray on the HPA axis was discernible.²⁹ To our knowledge, a similar demonstration of the safety of a nasally administered mometasone wash has not been performed. As a result, ten participants from each study arm will be selected for an optional cosyntropin test to assess the effect of mometasone nasal irrigation on the HPA axis.

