Baseline levels of serum cortisol will be measured at the subject's first visit. Subjects will then receive 0.25 mg of cosyntropin and 10 mg of mannitol reconstituted with 1 mL of 0.9% sodium chloride as an intramuscular injection to stimulate the adrenal cortex. Serum will be drawn 30 minutes and cortisol level measured. This test will be repeated upon the completion of 60 days of mometasone nasal irrigation or spray. If mometasone is absorbed systemically via nasal irrigation, serum cortisol should be inappropriately low upon cosyntropin stimulation compared to baseline. No change in serum cortisol is expected in the mometasone nasal spray group based on prior studies. The cosyntropin test will be performed at the Center for Outpatient Health and blood cortisol levels measured by the General Clinical Research Center Immunoassay Core Laboratory.

In the event that at the first pre-intervention cosyntropin visit, a post-stimulation level is below the critical level of 18 µg/dL, indicating an insufficient adrenal response, the PI will be notified and the study participant contacted. With an abnormal cortisol level pre-intervention, the study participant will not be eligible for further participation in the study and the study coordinator will recommend that the participant be evaluated by his/her primary care physician.

In the event that a post-stimulation level is below the critical level of 18 µg/dL indicating an insufficient adrenal response, the PI will be notified and the study coordinator will notify the patient and recommend a referral to the study participant's primary care physician. Study participants in either intervention arm will remain on the intervention until cosyntropin lab values are received and reviewed.

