***Scores**

Sinuses: 0= no mucosal thickening, 1= partial opacification, 2= total opacification

OMC: 0= not occluded, 2=obstructed

CT evidence of inflammation of the sinuses will be defined as mucosal thickening of at least one paranasal sinus and does not have to be severe enough to be classified as “partial opacification” or have a Lund and MacKay score of 1 or greater.

Data Collection

Sources of Research Material: All research-related information, including responses to the selected patient-reported outcome measures, will be captured electronically.. Week 2, Week 4, and Week 6 patient-reported outcome measures will be captured via an email sent to subjects with direct linkage to REDCap™ (Research Electronic Data Capture). All data will be stored in a specially designed database created by staff in the Clinical Outcomes Research Office using REDCap™. Patient confidentiality will be maintained through the use of unique patient ID.

Assessment of Treatment Efficacy: The change in the average SNOT-22 scores between baseline and eight weeks will serve as the primary outcome measure in this study and will be calculated as:

$$\text{Primary Outcome Measure, } \Delta\text{SNOT-22} = \text{SNOT-22}_{\text{baseline}} - \text{SNOT-22}_{\text{8-week follow up}}$$

To assess the trajectory of change within subjects randomized to the two treatment arms the baseline, two-week, four-week, six-week, and eight-week SNOT-22 assessment will be compared.

Assessment of Treatment Safety: As described above, 10 participants from each study arm will be selected for a cosyntropin test to assess for effects of mometasone nasal irrigation on the HPA axis. Treatment safety will also be assessed by patient interview and will include collection of adverse events experienced by the patient during the eight-week participation.

Risk Assessment: Mometasone has a potent glucocorticoid activity and weak mineralocorticoid activity. As an inhaled product, mometasone has an onset of action in 24 hours and peak effect between 1-4 weeks. The drug is well-tolerated and the more frequent side effects include: nose irritation, epistaxis, lightheadedness, and upset stomach. At recommended daily doses in both pediatric and adult patients, no adverse effects were seen on the HPA axis.²⁹

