To assess the time trajectory of change within subjects randomized to the two treatment arms, the baseline, 2 week, 4 week, 6 week, and 8 week SNOT-22 assessments will be computed and compared. Within group differences will be compared using a repeated measure ANOVA. A general linear model (GLM) approach will be used to explore through the testing of an interaction effect (treatment group x time) whether the magnitude and pattern of change in SNOT-22 scores at baseline, 2 weeks, 4 weeks, 6 weeks, and 8 weeks are different between the 2 treatment groups. In addition to allowing for exploration of the interaction effect, the GLM model allows for evaluation of estimated means after controlling for potential confounders. A robust regression model will be used if the assumption of the GLM model will not be met. The distribution of responses on the Clinical Global Impression (CGI) scale will be calculated within each intervention arm and the difference in responses between the two intervention arms will be compared for statistical significance with the chi-square statistic.

All statistical analyses will be performed with the appropriate statistical software e.g. SAS, SPSS. Statistical significance will be defined as a two-tailed test of significance p value of 0.05 or less.

Stopping rules based on the work of O'Brien and Fleming³⁸ for the conduct of clinical trials will be followed. An Intention-to-Treat analysis will be used for the final data analyses.

Sample Size Calculations: The sample size for this study was calculated based on achieving a difference of 9 points or more on SNOT-22 scores. Thus, to be able to detect with 80% power at the 2-sided alpha level of 0.05 a difference of 9 points or greater between the 2 treatment groups, a total of 50 subjects- 25 subjects per group- will be necessary. With an anticipated 15% drop out/non-compliance rate, the total sample size planned for this study will be 44 subjects.

Remuneration: Subjects will receive \$50 after baseline and \$50 at final visit and upon successful completion of trial.

For subjects who complete the coynstropin test, they will receive up to an additional \$100. Subjects will receive \$50 after the baseline cosyntropin test and another \$50 following the second cosyntropin test.

Timeline of the Study

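### Aim 2 expects no HPA effect, but study-drug use is never recorded, so a normal second cosyntropin result cannot be tied to exposure

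*Combined protocol and SAP*

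**What the plan says.** **Hypothesis.** Under Aim 2 (II. Specific Aims), "we hypothesize that MF nasal saline irrigation will have a negligible effect on the HPA axis". The same paragraph notes that, as far as the authors know, this has not been studied for a mometasone rinse.

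**Sample and timing.** Aim 2 says that "10 participants will be sampled from each study arm"; the Cosyntropin Test section makes the test voluntary: "ten participants from each study arm will be selected for an optional cosyntropin test". On the second test: "This test will be repeated upon the completion of 60 days of mometasone nasal irrigation or spray". An individual result is flagged when the "post-stimulation level is below the critical level of 18" µg/dL.

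**Analysis set.** The Statistical Analysis section ends with one rule: "An Intention-to-Treat analysis will be used for the final data analyses". No safety, as-treated or per-protocol set is named. The endpoints discussed in that section are SNOT-22 and the global impression scale; no cortisol estimate, test, interval or margin appears.

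**Exposure.** Patients get written instructions and a video (Intervention), and the pharmacy mails the products to them. The lists of variables, the Data Collection section and the Calendar of Events contain no diary, count, return of bottles or question about use. The calendar's intervention row shows when treatment is scheduled, not what was taken. On safety: "Treatment safety will also be assessed by patient interview and will include collection of adverse events experienced by the patient during the eight-week participation". Non-compliance appears only in the Sample Size paragraph: "With an anticipated 15% drop out/non-compliance rate".

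**The concern.** In a superiority comparison such as the SNOT-22 analysis, patients who do not take their treatment usually shrink the difference, so keeping them in is cautious. Where the hoped-for result is no change, the same patients shift the data towards that result.

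The Cosyntropin Test section argues that absorbed mometasone would show up as a low stimulated cortisol. A normal value is reassuring by that argument only if the drug was used. Nothing the plan collects can show that, and reliable usage data cannot be reconstructed once the trial is over.

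The daily routine is not trivial: purchased or boiled water, two capsules to dissolve, both sides to rinse, then two sprays per nostril. With ten patients per arm, each unrecognised non-user is a tenth of that arm's evidence.

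**Working it through.** The plan states no figure for Aim 2, so there is none to reproduce. What follows shows the scale of the problem under stated assumptions.

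**Inputs**
- Tested patients per arm: 10 (Aim 2; Cosyntropin Test). All ten are assumed to have a second test.
- Share of tested patients who used no drug, c: not in the documents. Assumed 5% to 15%. The top of the range takes the whole pooled 15% from the Sample Size paragraph as non-use among tested patients.
- Suppression rate among true users, p: not in the documents. 10% and 20% are used as illustrations.

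**1. Expected non-users per arm, 10 × c, and chance of at least one, 1 − (1 − c)^10**
- c = 5%: 0.5 expected; 1 − 0.95^10 = 40%.
- c = 15%: 1.5 expected; 1 − 0.85^10 = 80%.

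**2. Dilution of the mean change.** If non-users took nothing and so show no drug effect, the observed mean fall is (1 − c) times the fall in users: 95% of it at c = 5% and 85% at c = 15%. Partial use dilutes less.

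**3. What zero suppressed patients would rule out.** The exact two-sided 95% upper bound for 0 of n is 1 − 0.025^(1/n).

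| Truly exposed | Upper bound |
|---|---|
| 10 | 30.8% |
| 9 | 33.6% |
| 8 | 36.9% |

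Counting all ten as exposed when eight were would understate the bound by 36.9 − 30.8 = 6.1 percentage points.

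**4. Does removing non-users restore the chance of seeing a case?** At c = 15% there are on average 8.5 users among ten.

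| p | All 10 exposed: 1 − (1 − p)^10 | 15% non-use, all 10 kept: 1 − (1 − 0.85p)^10 | Users only: 1 − (1 − p)^8.5 |
|---|---|---|---|
| 10% | 65% | 59% | 59% |
| 20% | 89% | 84% | 85% |

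The last two columns agree to within a point. Non-users contribute no cases, so leaving them out adds none. Restricting the set corrects the denominator and the diluted mean, not the chance of detection.

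**5. Direction.** The pull towards no effect is clear for the change within an arm, provided any true effect lowers stimulated cortisol. Both arms receive mometasone. Equal non-use also shrinks the difference between arms; unequal non-use could move that difference either way.

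**The case against.** The strongest reply is that a reader might infer that the plan prescribes intention-to-treat for the cortisol analysis and so counts patients who never took mometasone as proof of its safety. The documents do not go that far. The sentence closes a section that deals with SNOT-22 and the global impression scale, and no cortisol analysis is described at all. That absence is the larger gap, and this part of the reply stands. It does not remove the problem: either the unqualified rule covers cortisol, or cortisol has no analysis set. In both cases exposure is unknown.

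Second, the follow-up test is tied to completing treatment, so most drop-outs would have no second value and could not dilute anything. This also stands, and it is why 15% is an upper reading. What remains is patients who come back having used little. Nothing described would identify them, and no usage condition is stated for the separate payment after the second test.

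Third, an adherent subset is chosen on behaviour after randomisation, which weakens the comparison between arms that Aim 2 states, and any cut-off for adequate use would have no source in the documents. That is a sound reason not to put such a subset in place of the full tested set. It is no reason to leave use unrecorded.

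Fourth, imprecision matters more: even with full use, 0 of 10 leaves rates up to 30.8% open. Agreed.

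**Conclusion.** The concern holds as a gap in data collection and reporting for Aim 2. Followed exactly, the plan would leave a normal second cosyntropin result that cannot be attributed to exposure, with any within-arm error favouring the hypothesis.

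The size is moderate: 0.5 to 1.5 expected non-users per arm, and a zero-event upper bound that moves from 30.8% to 33.6% or 36.9% if one or two of the ten were unexposed. These figures rest on the assumed 5% to 15% range, on ten completed second tests, and on non-users having taken nothing.

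Two stronger conclusions should not be drawn. The 15% is not a rate of non-use among patients who return for testing, because it pools drop-out with non-compliance for the whole trial. And an exposed-only analysis would not regain lost sensitivity; ten per arm sets that limit. The SNOT-22 analysis is unaffected. This is an inexpensive improvement worth making before the trial is run, not a flaw in the primary result.

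**What to change.** - **Record use.** Add an item asking on how many of the last seven days the irrigation and the spray were each used, to the existing week 2, 4 and 6 REDCap e-mails and to the week 8 visit. Asking everyone about both products preserves the blind. A bottle return or capsule count at week 8 is optional.
- **Specify the cortisol analysis.** Report the change in cortisol and the proportion below 18 µg/dL after stimulation, with 95% confidence intervals, for all tested patients and, beside it, for those with recorded use up to the second test. Fix the cut-off for adequate use before unblinding. Rest any statement of no HPA effect on both sets of results.
- **Leave SNOT-22 as it is**, under intention-to-treat.
- **Reconcile the timing.** The second test is placed after 60 days, while the intervention lasts 8 weeks (8 × 7 = 56 days) and the calendar puts the test at week 8. These passages must agree so that the usage window is defined.

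The cost is a short survey item, a few sentences of analysis text and slight extra burden on respondents. The exposed set may lose one or two patients per arm, with wider intervals.

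### The planned 44 subjects do not deliver the stated 80% power, and a pooled 15% head-count allowance is the wrong tool for non-compliance under intention-to-treat

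*Combined protocol and SAP*

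**What the plan says.** Three statements in section III of the combined protocol and SAP bear on this.

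- **Target.** Sample Size Calculations aims to "detect with 80% power at the 2-sided alpha level of 0.05" a stated margin: "a difference of 9 points or greater between the 2 treatment groups, a total of 50 subjects- 25 subjects per group- will be necessary".
- **Allowance.** The next sentence reads: "With an anticipated 15% drop out/non-compliance rate, the total sample size planned for this study will be 44 subjects". The 15% is one combined rate. It is not divided between drop-out and non-compliance, and non-compliance is not defined.
- **Analysis set.** Statistical Analysis states: "An Intention-to-Treat analysis will be used for the final data analyses".

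The primary test is an independent-samples t-test on the change in SNOT-22 from baseline to week 8. The Calendar of Events schedules a week-8 SNOT-22 with no compliance condition attached. The plan gives no SD for the change score and no rule for missing week-8 scores. Elsewhere it gives enrolment as up to 50, and study bottles are numbered 1 to 50.

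**The concern.** Drop-out and non-compliance act differently in an intention-to-treat comparison. A subject with no week-8 score lowers the number available to the t-test. A subject who does not take the drug but returns a week-8 score is analysed in the assigned arm, so the number is unchanged but the average difference between arms may fall. The plan treats both as one change in head count and leaves the 9 points as they were.

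The head count also moves the wrong way: an allowance for loss should raise 50, and here the figure drops to 44. A null result would be read against 80% power although the printed size does not provide it.

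**Working it through.** **Inputs from the plan.** Two-sided alpha 0.05; power 80%; difference 9 points; 25 per group; combined rate 15%; planned total 44, or 22 per group with equal allocation. The 9 points are taken on the 0–110 total scale, because a 9-point difference cannot occur on the 0–5 per-item average that the plan also describes.

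**Step 1: the plan's 50.** This cannot be checked directly because no SD is given. It can be back-solved. For a two-sample t-test with n per arm, df = 2n − 2 and the noncentrality is d × √(n/2). With n = 25, 80% power needs d = 0.8087 (noncentrality 0.8087 × √12.5 = 2.859), so SD = 9 / 0.8087 = 11.13. Once 25 per arm is accepted as giving 80%, the powers below depend only on n and on the fraction of the 9 points that remains.

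**Step 2: the plan's 44.** The usual allowance is 50 / (1 − 0.15) = 58.8, rounded up to 59. Multiplying instead gives 50 × 1.15 = 57.5, or 58. Neither is 44. The figure appears only if 50 is reduced: 50 / 1.15 = 43.5, rounded up to 44 (50 × 0.85 = 42.5 does not match). A transposition is also possible: starting from about 43 or 44 evaluable, 43 × 1.15 = 49.5, rounded up to 50.

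**Step 3: power at 44 as printed.** Let L be the share of randomised subjects with no week-8 score and f the share who are non-compliant but analysed. Then n = 22 × (1 − L) per arm. If non-compliers show no difference between arms and the SD is unchanged, the expected difference is 9 × [1 − f / (1 − L)].

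| Make-up of the 15% | n per arm | Difference | Noncentrality | Power |
|---|---|---|---|---|
| None occurs | 22 | 9 | 0.8087 × √11 = 2.682 | 74.6% |
| All drop out | 18.7 | 9 | 0.8087 × √9.35 = 2.473 | 67.2% |
| Half and half | 20.35 | 9 × (1 − 0.075/0.925) = 8.27 | 0.7431 × √10.175 = 2.370 | 63.7% |
| All retained non-compliers | 22 | 9 × 0.85 = 7.65 | 0.6874 × √11 = 2.280 | 60.5% |

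**Step 4: if the figures were transposed.** With 44 needed and 50 enrolled, 80% at 22 per arm implies d = 0.865 and SD 10.41. Power at 50 enrolled is then 78.6% if all 15% drop out (21.25 per arm), 75.3% for half and half (23.1 per arm, 8.27 points), and 72.1% if all are retained non-compliers (25 per arm, 7.65 points).

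**Step 5: does correcting the arithmetic settle it?** With 59 enrolled and SD 11.13, power is 80.1% if the whole 15% drop out, 76.9% for half and half, and 73.7% if all are retained non-compliers. Correct inflation therefore covers drop-out but not dilution.

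**The case against.** The strongest reply is that dilution may not arise at all. The target is "a difference of 9 points or greater between the 2 treatment groups", and 9 points is the plan's threshold for a clinically meaningful change, not a forecast for patients who take every dose. Read as the difference between groups as randomised, it already includes non-compliers and needs no reduction. This stands. A reader might infer that power is wrong even with 25 analysed per arm and nobody lost; the documents do not establish that.

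A reader might also infer that the plan excludes non-compliers, or defines two conflicting analysis sets. It does neither. The only analysis set named is intention-to-treat, and the sample-size paragraph merely pools the two events in one rate.

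Non-compliance is also undefined. It could mean missed visits or questionnaires, which is missing data, and a head-count allowance suits that.

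Finally, the dilution formula assumes equal, all-or-nothing non-compliance in both arms. This is an active-versus-active double-dummy design, and a subject who skips only the placebo component loses no drug. With assumed mean improvements of 20 and 11 points and no improvement in non-compliers, 15% non-compliance in both arms gives 7.65. In the spray arm alone it gives 20 − 11 × 0.85 = 10.65; in the irrigation arm alone, 20 × 0.85 − 11 = 6.0. Neither the sign nor the size of the effect is fixed by the documents.

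These points limit the dilution argument. They do not rescue the 80%: at 44, power is about 75% before any loss or non-compliance.

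**Conclusion.** The point holds in two parts of unequal certainty.

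**The printed size does not give the printed power.** If 50 are needed for 80%, 44 give about 75% at best, whatever the SD, and about 67% if the anticipated 15% drop out. This is the larger fault in the paragraph and does not depend on any view of compliance. If 50 and 44 were transposed and the 15% are all drop-outs, the shortfall nearly vanishes (about 79%).

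**A head-count allowance does not fit non-compliance under intention-to-treat, on either reading of the 9 points.** If 9 is the difference in all randomised subjects, retained non-compliers need no allowance. If 9 is the effect in compliers, they reduce the difference, not the number. On the second reading power at 44 falls to about 64% for a half/half split and 60% at the extreme. Treating the whole 15% as retained instead of lost therefore costs about 7 points (67.2% against 60.5%).

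The dilution figures assume no between-arm effect in non-compliers, equal shares in both arms and an unchanged SD. The plan states neither the split, the SD nor the effect in non-compliers, so they are ranges, not estimates of this trial's power.

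**What to change.** In Sample Size Calculations:

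1. Reconcile the 50 and the 44, give the SD and its source, and restate the power of the intention-to-treat t-test at the size actually planned.
2. Limit the head-count allowance to subjects expected to have no week-8 SNOT-22.
3. Define non-compliance, then choose one of two statements. Either say that 9 points is the difference among all randomised subjects and take non-compliance out of the allowance, or give the expected non-compliance share and the power for the correspondingly reduced difference.

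The cost is rewriting one paragraph. No extra patients are required; the stated power becomes less favourable.
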